1.2.3. Patient Disposition

Study completion and reasons for discontinuation for all randomized patients in the double-blind phase will be summarized for each treatment group. Discontinuations by reason will be tabulated by visit for each treatment group.

Time to discontinuation due to adverse events, lack of efficacy, and for any reason will be analyzed using Kaplan-Meier survival techniques; the log-rank test will be used for group comparison.

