This is multicenter, randomized, double-blind, placebo-controlled study to be conducted in the United States. Approximately Two Hundred (200) patients diagnosed with mild atopic dermatitis, who satisfy the eligibility criteria for the study, will be randomized to receive either tradipitant 85 mg or matching placebo BID.

The study is divided into two phases: the pre-treatment phase and the evaluation phase. The pre-treatment phase includes a screening and a baseline visit where patients' eligibility for the study will be assessed. Washout of medications will occur during the screening phase.

The evaluation phase includes 8 weeks of randomized, double-blind, placebo-controlled treatment. In-clinic evaluations will occur at Screening, Baseline, and Weeks 2, 4, 6, and 8.

Criteria for Evaluation:

Efficacy:

Efficacy assessments will include:

- Worst Itch Numerical Rating Scale (WI-NRS)
- SCORing Atopic Dermatitis (SCORAD) index
- Validated Investigator Global Assessment scale for Atopic Dermatitis (vIGA-AD)
- Eczema Area and Severity Index (EASI)
- Clinical Global Impression of Change (CGI-C)
- Patient Global Impression of Change (PGI-C)
- Patient Oriented Eczema Measure (POEM)
- Dermatology Life Quality Index (DLQI)
- Patient Benefit Index Pruritus (PBI-P)
- Insomnia Symptom Questionnaire (ISQ)
- Healthy Days Core Module (4 questions) (HRQOL-4)

Safety:

- Safety and tolerability assessments will include the recording of adverse events (AEs), physical examinations, clinical laboratory assessments, vital signs, and electrocardiograms.
- The Columbia-Suicide Severity Scale (C-SSRS) will be used to assess suicidal behavior and ideation.

Table 1: Schedule of Evaluations

Phase	Pre-Tre	Pre-Treatment		Evaluation				
Visit	V1 Screening	V2 Baseline	V3	V4	V5	V6		
Study Day	Up to Day -45	Day 0	Day 14 ¹	Day 28 ¹	Day 42 ¹	Day 56 ¹ or ET		
Informed Consent Form (ICF) ²	X							
Eligibility assessment	X	X						
Patient demography	X							
Medical history	X							
Prior/concomitant medications	X	X	X	X	X	X		
Adverse Event (AE) Assessment ³	X	X	X	X	X	X		
Serum β-HCG (for WOCBP)	X					X		
Urine pregnancy test (for WOCBP)		X	X	X	X			
HbA1c	X							
Hepatitis B/C screen	X							
Drug and alcohol screen	X	X	X	X	X	X		
Hematology, chemistry, and urinalysis ⁴	X	X	X	X		X		
Coagulation ⁴	X							
IgE collection	X	X	X	X	X	X		
Cytokine Panel ⁵	X					X		
Filaggrin Analysis ⁶	X							
Pharmacogenetic (PG) sample ⁶	X							
Pharmacokinetic (PK) sample		X	X	X	X	X		

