1. STATISTICS

1.1. Sample Size and Accrual

A total sample size of 200 patients (100 per arm) will provide approximately 93% power to detect a 25% response rate difference, assuming 30% and 55% response rates in placebo and VLY-686 treatment groups respectively, based on a two-sided Fisher's Exact Test with a 5% significance level. In addition, 200 patients will provide about 90% power to detect a 1.2-point treatment difference in worst itch score, as measured by WI-NRS, between VLY-686 and placebo with a standard deviation (SD) of 2.6, based on a two-sided Student's T-Test with a 5% significance level.

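### Kaplan-Meier curves for discontinuation due to adverse events or lack of efficacy will slightly overstate the proportion leaving for that cause, if other withdrawals are censored

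*SAP*

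**What the plan says.** SAP section 1.2.3 (Patient Disposition) states: "Time to discontinuation due to adverse events, lack of efficacy, and for any reason will be analyzed using Kaplan-Meier survival techniques". For the arms, "the log-rank test will be used for group comparison". The section gives no rule for patients who leave for a reason other than the one being analysed, and neither document mentions competing events or cumulative incidence.

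The same section also plans crude summaries: "Study completion and reasons for discontinuation for all randomized patients in the double-blind phase will be summarized for each treatment group", and "Discontinuations by reason will be tabulated by visit for each treatment group". SAP section 1.4.1 (Adverse Events) adds the proportion of patients in each group whose adverse events led to discontinuation. Follow-up is fixed. The Protocol synopsis says: "The evaluation phase includes 8 weeks of randomized, double-blind, placebo-controlled treatment".

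SAP sections 1.2 and 1.2.1 describe this text as general and leave the details to a fuller analysis plan, which is not among the documents.

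**The concern.** A patient who has left for one reason can no longer leave for another, so the reasons compete. A Kaplan-Meier curve for one cause, with other withdrawals censored, describes a hypothetical setting in which nobody leaves for any other reason. Read as the share of patients who actually discontinued for adverse events or lack of efficacy, one minus that curve is too high whenever other withdrawals occur. The excess grows with the amount of other withdrawal.

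At stake is a descriptive display of tolerability and of withdrawal for lack of efficacy. The curve would not match the crude table beside it, and nothing in the plan would explain why. If other withdrawals are more common in one arm, the excess also differs by arm.

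**Working it through.** **Inputs.** From the documents: 100 patients per arm (SAP 1.1), 8 weeks of fixed follow-up (Protocol synopsis), and Kaplan-Meier with a log-rank test (SAP 1.2.3). Assumed: the discontinuation rates, constant hazards over the 8 weeks, and censoring of other withdrawals. The plan has no discontinuation figure to reproduce. Its responder power statement (about 93% by Fisher's exact test, 30% against 55%) recomputes to 93.9% and plays no part in this point.

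**1. Overstatement within an arm.** Let h1 be the cumulative hazard over 8 weeks for the cause of interest and h2 that for all other reasons.

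- True cumulative incidence = h1/(h1+h2) × [1 − exp(−(h1+h2))]
- One minus Kaplan-Meier = 1 − exp(−h1)

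If a proportion T leaves in total, h1+h2 = −ln(1−T). Example with T = 20% and a cause share of 30%: h1+h2 = 0.2231 and h1 = 0.0669. The true incidence is 0.30 × 20% = 6.0%, and the curve reads 1 − exp(−0.0669) = 6.5%.

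| Total leaving | Cause share | True incidence | 1 − KM | Excess (points) |
|---|---|---|---|---|
| 5% | 20% | 1.00% | 1.02% | 0.02 |
| 10% | 30% | 3.0% | 3.1% | 0.1 |
| 20% | 30% | 6.0% | 6.5% | 0.5 |
| 30% | 30% | 9.0% | 10.2% | 1.2 |
| 40% | 30% | 12.0% | 14.2% | 2.2 |
| 40% | 50% | 20.0% | 22.5% | 2.5 |

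Over totals of 5% to 40% and shares of 20% to 50%, the excess runs from 0.02 to 2.5 points (ratio 1.01 to 1.21).

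**2. Equal cumulative incidence, unequal other withdrawal.** In each scenario h1 was solved so that both arms have the same true incidence at Week 8. The log-rank test was simulated with 100 per arm and 10,000 runs.

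| True incidence, both arms | Other-cause hazard by arm | 1 − KM by arm | Hazard ratio for the cause | Log-rank rejection |
|---|---|---|---|---|
| 5% | 0.05 / 0.20 | 5.12% / 5.51% | 1.08 | 5.2% |
| 5% | 0.10 / 0.30 | 5.25% / 5.78% | 1.10 | 5.3% |
| 5% | 0.05 / 0.40 | 5.12% / 6.05% | 1.19 | 6.1% |
| 10% | 0.05 / 0.20 | 10.25% / 11.01% | 1.08 | 5.4% |
| 10% | 0.10 / 0.30 | 10.50% / 11.54% | 1.11 | 5.3% |
| 10% | 0.05 / 0.40 | 10.25% / 12.08% | 1.19 | 6.8% |

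The curves separate by 0.4 to 1.0 point under the milder imbalances and by up to 1.8 points in the extreme case. Rejection above 5% is not a false-positive rate here, because the cause-specific hazards really differ.

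**3. Equal cause-specific hazards, unequal other withdrawal.** With h1 = 0.05 or 0.10 in both arms and the same other-cause hazards, 1 − KM is identical in the arms and the log-rank test rejects in 4.6% to 4.9% of runs. The cumulative incidences differ by 0.3 to 1.4 points. For example, h1 = 0.10 with other hazards 0.05 / 0.40 gives 9.3% against 7.9%. Here the Kaplan-Meier curves hide a gap that exists on the incidence scale.

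**The case against.** The strongest reply is that the plan already supplies the right numbers. With fixed 8-week follow-up, the crude proportion leaving for each reason estimates cumulative incidence at Week 8, and the by-visit tabulation does so at each visit. SAP 1.4.1 gives the proportion with adverse events leading to discontinuation a second time. This stands, and it is why the point is minor. A reader might infer that tolerability would be judged from the curves alone, but the documents do not support that. What remains is that the curve and the table would disagree, and that the time course between visits would come only from the curve.

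Second, censoring is inferred. SAP 1.2.3 does not state it, and the fuller plan might set another rule. This also stands, so the point is conditional. Still, the section already names the estimator, and censoring other exits is what that name ordinarily implies.

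Third, a reader might infer that the planned test will find differences that do not exist. It will not. If competing withdrawals are censored, the log-rank test is a valid test of equal cause-specific hazards. The spurious gap exists only on the cumulative-incidence scale, and the documents do not say which scale is of interest.

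Fourth, a reader might infer that the single-cause curves must add up to more than the any-reason curve. That requires a curve for every reason, and this plan has only two. With assumed true rates of 5% for adverse events, 5% for lack of efficacy and 15% for other reasons, T = 25% and each planned curve reads 1 − 0.75^(5/25) = 5.6%. They total 11.2%, well under 25%.

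Last, the effect is small beside sampling error. At 8% per arm with 100 patients each, the standard error of a difference is √(2 × 0.08 × 0.92/100) = 3.8 points. This also stands.

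**Conclusion.** The point holds as a minor one. If withdrawals for other reasons are censored, one minus Kaplan-Meier is the wrong estimator of the proportion discontinuing for adverse events or for lack of efficacy, and it errs upwards. Under the assumed rates and constant hazards, the excess is about 0.02 to 2.5 points. At a total of 20% or less it is below 0.6 point. The documents give no dropout rate, so the place in that range is unknown. A misleading gap between arms, or a hidden one, needs other withdrawals to differ by arm, and nothing in the documents says that they will.

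The any-reason Kaplan-Meier analysis, the validity of the log-rank test for cause-specific hazards, the primary endpoint, the significance level and the sample size are all unaffected.

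**What to change.** In SAP 1.2.3:

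- For discontinuation due to adverse events and due to lack of efficacy, replace one minus Kaplan-Meier with Aalen-Johansen cumulative incidence by arm, treating other reasons for leaving as competing events.
- Keep the log-rank test for these two outcomes, state that other withdrawals are censored in it, and label it as a comparison of cause-specific hazards. Gray's test is needed only if the arms are to be compared on the incidence scale.
- Keep Kaplan-Meier and the log-rank test for discontinuation for any reason.

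The cost is a line or two of wording and a standard programming option. No additional data are needed, because the reason for discontinuation is already to be summarised. The curves would then agree with the planned crude tables.

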1.2.4. Demography and Other Baseline Data

Demographic data and patient characteristics at screening/baseline will be listed and summarized by treatment group for all randomized patients using descriptive statistics.

Past and current medical history will be summarized by treatment group using the system organ class (SOC) as coded using the Medical Dictionary for Regulatory Activities (MedDRA) coding dictionary.

Past medical conditions will be defined as an onset date prior to randomization (Visit 2) and resolved (not on-going) as of Visit 2. Current medical conditions, defined as an onset date on or after the date of randomization (Visit 2) or an onset date prior to randomization (Visit 2) and unresolved (on-going) as of Visit 2, will be reported separately, but similarly to the past medical conditions. If both a past and a current (on-going) medical condition record are indicated for a condition, the condition will be presented under current medical conditions only.

1.2.5. Study Medication

The number of patients at each visit will be summarized by treatment group.

The compliance to study medication, as recorded in the CRF, will also be summarized by treatment group. The proportion of patients who are significantly noncompliant in the double-blind phase, as noted in [Section 9.3](#) of this protocol, will be summarized by treatment groups.

1.2.6. Prior/Concomitant Therapy

Any medications or therapy present before the first dose of study medication (Visit 2) will be considered as prior medications. Concomitant medications (medications present while on study medication) will be recorded throughout the study and at early discontinuation. These medications will be coded using the WHO-drug dictionary. The number of patients from the Safety Population using prior or concomitant medications will be categorized by the WHO-drug category and preferred term, and presented for each treatment group. In any given category (e.g., drug category), a patient will be counted only once.

1.3. Efficacy Data Analysis

1.3.1. Primary Outcome and Methodology

The primary efficacy outcome measure for the double-blind phase will be the WI-NRS responder rate at Week 2. A WI-NRS (worst itch numerical rating scale) responder is defined as a patient achieving at least 4 points reduction from baseline in WI-NRS. The primary statistical method will be the CMH (Cochran–Mantel–Haenszel) test. A detailed description of the primary analysis model and the corresponding sensitivity analysis will be included in the SAP.

As stated previously, any changes in the statistical methods that occur prior to database lock will be documented in the SAP and will not require a protocol amendment.

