1.2. Statistical Methods and Analysis Plan

This section describes the planned statistical analyses in general terms. A complete description of the methodology will be specified in a statistical analysis plan (SAP). Any changes in the statistical methods described in this protocol that occur prior to database lock will be documented in the SAP and will not require a protocol amendment.

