1.2.1. General

Statistical analyses will be performed using two-sided tests.

Data will be summarized by treatment group (and by visit when applicable), with respect to demographic and baseline characteristics, efficacy variables, and safety variables.

Summary statistics will include the mean, N, standard deviation, median, minimum, and maximum values for continuous variables, and frequencies and percentages for categorical variables.

For the analyses of change from baseline, only patients with a baseline and at least one (1) post-baseline measure will be included in the analysis. Unless otherwise specified, baseline is defined as the latest non-missing observation across all the visits in the screening phase before the active study drug begins. Endpoint will be the latest non-missing observation across all the post-baseline visits in the evaluation phase.

Low enrolling sites will be pooled for analysis and the pooling algorithm will be determined prior to breaking the blind. The goal of pooling low enrolling sites is to have a sufficient number of patients per treatment group within a site for the analysis models and for the evaluation of the treatment-by-site interaction for the primary endpoint. Unless otherwise specified, the pooled sites will only be used in the analyses where the site has an effect. The actual sites rather than the pooled sites will be specified in the data listings.

Details of the model and the analyses will be specified in the SAP. All statistical analyses will be performed using SAS®, Version 9.1.3 or higher.

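### Does the primary CMH test give away power because no baseline WI-NRS stratum or covariate is named for it?

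*SAP*

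**What the plan says.** Section 1.3.1 of the SAP makes the Week 2 WI-NRS responder rate the primary outcome. A responder is "a patient achieving at least 4 points reduction from baseline in WI-NRS". On the test it says "The primary statistical method will be the CMH" test, with no strata or covariates listed.

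The text supplied as the SAP is a summary that points to a fuller plan:

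- Section 1.2: "This section describes the planned statistical analyses in general terms".
- Section 1.2.1: "Details of the model and the analyses will be specified in the SAP".
- Section 1.3.1: "A detailed description of the primary analysis model and the corresponding sensitivity analysis will be included in the SAP".

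The one factor tied to the models is site. Section 1.2.1 pools low-enrolling sites "to have a sufficient number of patients per treatment group within a site for the analysis models". Section 1.1 bases the sample size on an unadjusted comparison: 100 patients per arm give "approximately 93% power to detect a 25% response rate difference" (30% versus 55%, Fisher's exact test, two-sided 5%). It adds a supporting t-test calculation for 1.2 points "with a standard deviation (SD) of 2.6".

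**The concern.** The responder definition is relative to baseline. Under inclusion criterion 5 of the protocol synopsis, visit scores at entry run from 5 to 10. A patient entering at 5 must reach 1 or below to respond, while one entering at 10 need only reach 6. Baseline WI-NRS is therefore a natural prognostic factor, and every eligible patient already has it. A primary test that ignores a prognostic factor can lose power, and adding one costs only a line of text if done before unblinding. Only efficiency would be at stake. The validity of the test and the sample size are not in question.

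**Working it through.** **1. The plan's own power figures.** Inputs from SAP 1.1: 100 per arm, 30% versus 55%, two-sided 5%; 1.2 points, SD 2.6.

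- Fisher's exact test, full enumeration: 93.9% (stated: about 93%).
- Pooled z: [0.25 - 1.96 × √(2 × 0.425 × 0.575/100)] / √(0.30 × 0.70/100 + 0.55 × 0.45/100) = (0.25 - 0.1370)/0.0676 = 1.67, so 95.3%.
- Unstratified CMH, exact enumeration: 95.5% without continuity correction, 93.9% with it.
- t-test: 1.2/(2.6 × √(2/100)) = 3.26. The normal approximation gives Φ(3.26 - 1.96) = 90.4%; the noncentral t gives 90.1% (stated: about 90%).

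Both stated figures hold with no baseline adjustment.

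**2. Validity.** The CMH statistic is [Σ(a - n₁m/n)]² / Σ[n₁n₀m(n - m)/(n²(n - 1))], summed over strata. Here a is the number of responders on active drug, m all responders, n₁ and n₀ the arm sizes, and n the stratum size. Simulated type I error is 4.8-5.1% unstratified and 4.9-5.1% with three baseline categories.

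**3. Effect of adding baseline.** The documents give neither the slope of change on baseline nor a baseline SD, so both are assumed. A slope of 0 makes change unrelated to baseline. A slope of 1.0 makes the Week 2 score unrelated to baseline. Taking 2.6 as the SD of the change score is a further assumption, because SAP 1.1 does not say whether it refers to the score or the change. The implied correlation is r = slope × baseline SD / 2.6; for example 0.7 × 1.35/2.6 = 0.36.

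The table shows the change in power (percentage points) against unstratified CMH at 30% versus 55%. Each test is size-corrected to 5%, with 30,000 trials per setting and a Monte Carlo standard error of about 0.1.

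| Baseline score (assumed SD) | Method | slope 0 | 0.4 | 0.7 | 1.0 |
|---|---|---|---|---|---|
| Visit, 5-10 (1.35) | CMH, 3 categories | -0.5 | +0.1 | +0.7 | +2.0 |
| | Standardised logistic | -0.3 | +0.2 | +1.0 | +2.3 |
| Visit, 5-10 (1.06) | CMH, 3 categories | -0.4 | -0.1 | +0.2 | +0.9 |
| | Standardised logistic | -0.3 | 0.0 | +0.4 | +1.3 |
| Diary average, 7-10 (0.74) | CMH, 3 categories | -0.6 | -0.5 | 0.0 | +0.4 |
| | Standardised logistic | -0.4 | -0.3 | +0.2 | +0.6 |

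A separate latent-normal simulation agrees. CMH with 2 to 4 baseline strata changes power by -0.3 to -0.6 at correlation 0, by +0.3 to +0.4 at 0.3 and by +2.3 to +2.7 at 0.6. For the stratified CMH, break-even lies between correlations of 0.2 and 0.3. On the diary score, even slope 1.0 gives only 0.74/2.6 = 0.28.

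**4. Against the comparator the SAP points to.** CMH is a stratified method, and pooled site is the only factor mentioned. Crossing 3 baseline categories with 10 assumed sites makes 30 strata, about 200/30 = 6.7 patients each. The change against CMH by site, at 30% versus 55%:

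| Baseline score (SD) | No site effect, slopes 0/0.4/0.7/1.0 | Assumed site SD 0.8 |
|---|---|---|
| Visit (1.35) | -2.4/-2.0/-0.8/+1.0 | -2.2/-1.6/-0.5/+0.9 |
| Visit (1.06) | -2.3/-1.7/-1.3/-0.2 | -2.1/-1.6/-0.9/+0.1 |
| Diary (0.74) | -2.7/-2.2/-2.0/-1.7 | -2.3/-2.0/-1.8/-1.6 |

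Power falls in 11 of 12 settings without a site effect and in 10 of 12 with one. Replacing site by baseline gives +0.7 to +3.1 with no site effect and -0.6 to +2.0 with site SD 0.8.

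**The case for a change.** The strongest argument for baseline adjustment is asymmetry. The CMH form costs at most about 0.6 points at the planned effect. If the true effect is smaller, say 30% versus 47.5%, unstratified power is only 71.9-72.9%, and three baseline categories can add up to 6.4 points (logistic, 7.4) for a worst loss of 0.8. Wider assumptions give more: a uniform 5-10 baseline (SD 1.71) gains up to 3.7 points at the planned effect and about 10 at 30% versus 50%.

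The arithmetic stands, but its conditions are demanding. The +6.4 needs slope 1.0 and visit SD 1.35 together. With SD 1.06 the maximum is +3.0, and with the diary average +1.6. At slopes 0.4 to 0.7 the range is -0.1 to +2.3. An SD of 1.35 exceeds that of a uniform 7-10 score (1.12), so it normally needs an appreciable share of patients at 5 or 6. Inclusion criterion 6, a diary worst-half average of at least 7, makes that less likely without excluding it. The smaller effects are themselves assumptions outside the plan.

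The logistic form also has a price. Its type I error is 5.1-5.4% with a small-sample variance factor and 5.0-5.8% without. Where the CMH is stratified by site, a gain is likely only if baseline replaces site. The text available does not say whether randomisation is stratified by site, which bears on whether site could be dropped.

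It also stands that the strata must be fixed before unblinding. Section 1.3.1 already assigns the detailed primary model to the fuller plan, which is not available here.

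**Conclusion.** The concern does not hold. The missing strata are a detail that the SAP expressly defers, and the test as written is valid with the power claimed for it. At the planned effect, three baseline categories move a power of about 95% by -0.6 to +2.0 points (logistic -0.4 to +2.3). At moderate slopes the range is -0.5 to +0.7 (logistic -0.3 to +1.0). These ranges span zero and rest on an assumed slope, an assumed baseline SD and the reading of 2.6 as the SD of change. Against a site-stratified CMH, crossing in baseline generally loses power. Statisticians may reasonably differ on whether to adjust for baseline here, and nothing in the documents shows that the plan's choice is inferior.

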1.3.2. Secondary Efficacy Analysis

The secondary efficacy outcomes include:

- WI-NRS;
- DDSS;
- Itch questionnaires including diary WI-NRS and VRS;
- WI-NRS responder at other time points;
- SCORAD;
- EASI;
- Proportion of patients with improvement on SCORAD index of at least 50%, 75% or 90% improvement;
- Proportion of patients with improvement on the EASI of at least 50%, 75% or 90% improvement;
- vIGA-AD;
- PGI-C;
- CGI-C;
- PBI-P;
- HRQOL-4;
- POEM;
- DLQI;
- ISQ;
- Pharmacokinetic-Pharmacodynamic correlation.

Continuous endpoints will be summarized and analyzed using MMRM (mixed effects model repeated measurement). Categorical endpoints will be analyzed by a CMH test. Details of the analysis will be described in the SAP.

Time to event data will be analyzed using the Kaplan-Meier method, and the treatment group differences will be tested by the log-rank test. Details of the analysis will be described in the SAP.

